11.4 Data Safety Monitoring Board

In the event of any questions or matters related to the disclosure policy in publications or in the informed consent document, an External Advisory Committee will be assembled, as needed, and will be comprised of members who are not affiliated with 1) the Department of Medicine; 2) neither the adaptive weight loss study and/or 3) Fitbit.

12. ADMINISTRATIVE PROCEDURES

12.1 Registration Procedures

For potential patients of this study, study teams are asked to inform the Coordinating Center of the date and time that the patient will need to be registered.

For non-Hopkins participating sites, all registration materials should be redacted/de-identified and received at least 24 hours prior to when eligibility confirmation is needed (submissions after 4pm will be considered received the next business day). Submit via encrypted email to the following:

- Protocol Chair ([name]): [contact]
- JH Coordinating Center (HBT and [name]):
 - o [contact]
 - o [contact]

Subjects will be registered with the study coordinator at the coordinating center (Johns Hopkins) once an informed consent form is signed. After eligibility is established, the Coordinating Center study coordinator will assign a study number. Subjects will not begin protocol-specified treatment until eligibility is confirmed and the patient is assigned a study number.

Upon review of the registration documents, the Coordinating Center at Johns Hopkins will confirm successful registration by return encrypted email to the local study team/designee.

12.2 Protocol Amendments

Any changes to the protocol will be made in the form of an amendment and must be approved by the IRB before implementation.

Amendments will be distributed by the coordinating center of the lead institution (Johns Hopkins) to all affiliate sites upon approval by the Johns Hopkins IRB. Requests or questions from sub-sites regarding study documents (such as to obtain a missing document) can be submitted through the coordinating center

12.3 Informed Consent

The investigator (or his/her designee) will explain to each subject the nature of the project, its purpose, the procedures involved, the expected duration, the potential risks and benefits involved and any discomfort it may entail. Each subject will be informed that participation in the project is voluntary and that he/she may withdraw from the project at any time and that withdrawal of consent will not affect his/her subsequent medical treatment or relationship with the treating physician or institution. The informed consent will be given by means of a standard written statement, written in non-technical language, which will be IRB approved. The subject should read and consider the statement before signing and dating it, and will be given a copy of the document. No subject will enter the project before his/her informed consent has been obtained.

In accordance with the Health Insurance Portability and Accountability Act (HIPAA), the written informed consent document will include a subject authorization to release medical information to the project sponsor and supporting agencies and/or allow these bodies, a regulatory authority, or Institutional Review Board access to subjects' medical information that includes all hospital records relevant to the project, including subjects' medical history. Our protocol does not contain any proprietary (nonpublic) information from an industry sponsor.

12.4 Ethics and Good Clinical Practice

This study must be carried out in compliance with the protocol and Good Clinical Practice, as described in:

- ICH Harmonized Tripartite Guidelines for Good Clinical Practice 1996.
- US 21 Code of Federal Regulations dealing with clinical studies (including parts 50 and 56 concerning informed consent and IRB regulations).
- Declaration of Helsinki, concerning medical research in humans (Recommendations Guiding Physicians in Biomedical Research Involving Human Subjects, Helsinki 1964, amended Tokyo 1975, Venice 1983, Hong Kong 1989, Somerset West 1996).

The investigator agrees to adhere to the instructions and procedures described in it and thereby to adhere to the principles of Good Clinical Practice that it conforms to.

12.5 Regulatory Authorities

Information regarding study conduct and progress will be reported to the JHM IRB per the current institutional standards. This trial does not use a medication, device, or product which requires FDA oversight and no reporting is required with regards to the clinical trial outlined at

this time. The protocol will be submitted to the NCI for its registration with Clinical Trials Registration Program (CTRP).

12.5.1 JHM Single IRB

Johns Hopkins Medicine is serving as the single IRB for this study. It is the preference of Johns Hopkins Medicine IRB to use the SMART IRB reliance agreement as the basis of reliance. The SMART IRB master reliance agreement was created in 2016 to harmonize and streamline the IRB review process for multisite studies. It enables reliance on a study-by-study basis, clearly defines roles and responsibilities of relying institutions and reviewing IRBs, and eliminates the need to sign reliance agreements for each study [e.g., a non-SMART IRB agreement]. 900+ institutions have already signed onto this agreement and are actively using it as the basis of reliance for multisite projects. Sites that will rely on JHM IRB are still responsible for conducting a local context review prior to the start of research at their site and for following any local and institutionally required policies as it applies to research at their site [e.g., reporting of unanticipated problems].

13. DATA ANALYSIS AND STATISTICAL CONSIDERATIONS

13.1 Study Design

This is a prospective, non-randomized clinical trial assessing the effects of the addition of pharmacotherapy to a behavioral weight loss intervention in overweight/obese breast cancer patients on an AI who are unable to attain at least 5% weight loss after 8 weeks of lifestyle intervention alone.

All enrolled patients will participate in a 6-month BWL program. At week 9, patients who achieve ≥5% weight loss from baseline will continue with BWL (FAST-BWL). Those failing to achieve a minimum of 5% weight loss will receive Contrave in addition to BWL (SLOW-BWL). After a 4-week titration of Contrave, SLOW-BWL will have their drug adherence logs and any new symptoms reviewed by the Protocol Chair and/or co-investigators. The participants will be prescribed the constant dose for 3 months until the end of study (drug will be shipped to patient's home).

The primary endpoint of this study is the proportion of SLOW-BWL patients who achieve at least 5% weight loss of their enrollment baseline weight at 6 months with the addition of Contrave to BWL. We anticipate 55% of 55 subjects enrolled will be in the SLOW-BWL group, resulting in a sample size of approximately 30 SLOW-BWL women and 25 FAST-BWL women.

The secondary endpoints include baseline, 2 and 6 months values in all participants for the following: cardiometabolic biomarkers (fasting glucose, fasting lipids, fasting insulin, adiponectin and leptin levels), genotypes, microbiome composition, body composition, patient-reported outcomes (PROs), and physical activities.

Simon's two-stage minimax design will be used for the SLOW-BWL group. The null hypothesis that the true rate of attaining $\geq 5\%$ weight loss is 10.9%, which is chosen based on the rate of

women attaining \geq 5% weight loss in the self-directed arm in the POWER-remote study.⁴ In the first stage, 15 SLOW-BWL women will be accrued. If there is 1 or fewer woman out of the 15 women who attain \geq 5% weight loss of their baseline weight, the study will be stopped. Otherwise, 15 additional SLOW-BWL women will be accrued for a total of 30 SLOW-BWL patients. The study does not plan to hold enrollment or treatment for the interim analysis. The null hypothesis will be rejected if 7 or more women are observed in the 30 patients who attain \geq 5% weight loss. This design yields a power of 80% at type I error rate of 5% when the true rate of attaining \geq 5% weight loss of the baseline weight for the SLOW-BWL women is 29%, a clinical meaningful rate for the SLOW-BWL women group.

Our results will inform us of how to better treat obesity in this vulnerable group of breast cancer patients. It may allow us to develop larger adaptive trials to assess long term breast cancer and non-cancer outcomes of behavioral interventions that incorporate pharmacotherapy. Additionally, our results may shed light on other modulators or obesity, such as biomarkers and the microbiome, laying foundation to future trials investigating additional interventions in breast cancer survivors who struggle with weight loss.

13.2 Analysis Plans

Data will be summarized using descriptive statistics (continuous data) and/or contingency tables (categorical data) for demographic and baseline characteristics, efficacy measurements at 2 and 6 months, and safety measurements throughout the study.

For the primary analysis, the study will be considered successful if there are 7 or more SLOW-BWL patients who could achieve more than 5% weight loss compared to their baseline weight, which implies that the success rate regarding to >=5% weight loss will be significantly higher than 10.9%.

Univariate analysis will be conducted to compare outcomes at different time points including baseline, 2 months and 6 months, and to compare outcomes from different groups including SLOW-BWL patients who attain ≥5% weight loss or <5% weight loss of their enrollment baseline weight at 6 months and FASE-BWL patients. Wilcoxon rank sum and Wilcoxon sign rank tests will be conducted when appropriate. Student's t-test will also be performed when the outcomes are normally distributed after necessary data transformation. Moreover, mixed effect regression analysis will be conducted to evaluate the longitudinal trend in the outcomes at different time points.

Furthermore, multivariate logistic regression analysis will be conducted to evaluate the effect of the baseline characteristics on attaining \geq 5% weight loss of the baseline weight at 2 months among FAST- and SLOW-BWL patients, and to evaluate the effect of the baseline characteristics and the weight loss at 2 months on attaining \geq 5% weight loss of the baseline weight at 6 months for SLOW-BWL patients.

The primary analysis dataset will be based on the intent-to-treat population. Analysis based on the per-protocol population will also be conducted as exploratory analysis. Missing data will be handled by multiple imputation and sensitivity analysis.

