4.3 Exploratory

- 4.3.1 To assess the proportion of women in the FAST-BWL arm who maintain \geq 5% weight loss at 6 months.
- 4.3.2 To describe baseline characteristics (cardiometabolic and obesity biomarkers, microbiome composition, PROs, demographics) of FAST-BWL vs SLOW-BWL, as well as participants who achieve ≥5% weight loss at 6 months vs those who are unable to.
- 4.3.3 To assess prevalence of AA genotype of MnSOD in breast cancer survivors with excess weight and if a greater proportion of women with the AA genotype achieve ≥5% weight loss and improvement in biomarkers at 6 months compared to the women who do not.
- 4.3.4 To determine if women who display the AA genotype of MnSOD and undergo addition of Contrave to BWL have greater weight loss compared to women who do not receive Contrave.

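### The 6-month predictor model in SLOW-BWL has about 9 events in 30 women; regressing percentage weight change on a few pre-named predictors would be a cheap improvement

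*Combined protocol and SAP*

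**What the plan says.** Section 13.2 plans two multivariable logistic models in one sentence, which opens "multivariate logistic regression analysis will be conducted to evaluate the effect of the baseline characteristics".

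- The first model is for reaching 5% loss at 2 months, among FAST-BWL and SLOW-BWL women together.
- The second is for SLOW-BWL women only, at 6 months. It is to "evaluate the effect of the baseline characteristics and the weight loss at 2 months on attaining" 5% loss.

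Neither model has a predictor list, a cap, a selection rule or a penalised or exact method. The nearest description of the candidate pool is exploratory objective 4.3.2: "To describe baseline characteristics (cardiometabolic and obesity biomarkers, microbiome composition, PROs, demographics". Secondary objective 4.2.1 names seven cardiometabolic markers.

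Section 13.1 expects 55% of 55 women to be slow responders, "resulting in a sample size of approximately 30 SLOW-BWL women and 25 FAST-BWL women". The Simon design there takes as its alternative a rate of "weight loss of the baseline weight for the SLOW-BWL women is 29%, a clinical meaningful rate".

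Section 7.4.1 has staff weigh each woman, in duplicate, at baseline, week 9 and the end of the study. The only other regression in 13.2 is a mixed model for the trend of outcomes over time. It is not said to relate baseline predictors to weight change.

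**The concern.** The second logistic model has few events, and it reduces a measured quantity to a yes/no split at 5%. Both cost power, and few events also push odds ratios away from 1 and widen their intervals.

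The model bears on which slow responders reach 5% after Contrave is added, which is close to secondary objective 4.2.2. Section 13.1 says the results may lead to larger adaptive trials. A weak or inflated predictor could be carried into those trials, and a real one could be missed.

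**Working it through.** **1. The plan's own design reproduces.** Inputs from 13.1: null rate 10.9%, alternative 29%, 15 women in stage 1 (stop at 1 or fewer responders), 30 in total (success at 7 or more).

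P(success) = Σ over x₁ ≥ 2 of P(X₁ = x₁) × P(X₂ ≥ 7 − x₁), where X₁ and X₂ are binomial with n = 15.

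- At 10.9%: 0.0378, within the stated 5%.
- At 29%: 0.8006, matching the stated 80%.

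**2. Events in the 6-month SLOW-BWL model.** Events = 30 × rate.

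- Design rate: 30 × 0.29 = 8.7
- Success cut-off: 7
- Null rate: 30 × 0.109 = 3.3

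At a true 29%, the 10th to 90th percentile range is 6 to 12 events. The chance of fewer than 10 is 0.64. Section 13.4 counts dropouts as not reaching 5%, which can only lower the count.

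**3. Events per predictor.** The plan gives no number of predictors, so this is a range.

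- 3 predictors: 7/3 = 2.3 to 8.7/3 = 2.9
- 8 predictors (for example the seven markers in 4.2.1 plus 2-month loss): 7/8 = 0.9 to 8.7/8 = 1.1

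**4. Logistic against linear, by simulation.** All of the following is assumed, because the documents give no figures for it: 30 women, independent standard-normal predictors, one of them correlated r with a normally distributed weight loss, the loss cut so that 29% respond, and two-sided 5% Wald tests. A failed fit counts as no detection. Monte Carlo error is about 1.5 points.

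| r | Covariates | Power, logistic | Power, linear |
|---|---|---|---|
| 0.5 | 3 | 44% | 82% |
| 0.5 | 5 | 37% | 74% |
| 0.5 | 8 | 19% | 72% |
| 0.4 | 3 | 30% | 59% |
| 0.4 | 5 | 24% | 54% |
| 0.4 | 8 | 12% | 49% |
| 0.3 | 5 | 15% | 32% |

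At r = 0.5, separated or non-converged logistic fits are about 1% with 3 covariates, 4% with 5 and 19% with 8. With one or two they are 0.2% or less.

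**5. Size of the estimates at r = 0.5.** The true odds ratio is about 2.7 per SD.

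| Covariates | Median estimated odds ratio | Median ratio of upper to lower 95% limit |
|---|---|---|
| 3 | 3.3 | 12 |
| 5 | 3.7 | 16 |
| 8 | 4.4 | 33 |

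**6. If the response is better than planned.** At a true rate of 50% there are about 15 events. With 5 covariates and r = 0.5, power is 50% logistic against 77% linear.

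**7. The 2-month model.** With 55 women, about 25 events and r = 0.5, logistic power is about 84% or higher with 3 to 8 covariates, and failed fits are at most 0.2%.

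**The case against.** **The 5% threshold is what the trial is about.** It defines the primary endpoint and frames the hypotheses and objectives. A model of who reaches it answers the question as asked, whereas mean percentage change is a different quantity. This stands, and it is why the 5% model should be kept. Objective 4.2.2 is also covered by the Wilcoxon and t-tests in 13.2, so the logistic model is supplementary.

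**The simulation favours linear regression.** The normal, linear set-up suits it, and r = 0.5 is a strong predictor. At r = 0.3 the linear model is also underpowered. This stands as a limit on what the change can deliver. The linear model still had the higher power in every setting tried.

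**Dropout is left out.** Section 10.2.6 cites attrition of 42% to 50% in the phase III Contrave trials. With 30% random dropout (assumed), a complete-case linear model with 5 covariates at r = 0.5 falls to about 52% power; the logistic model falls too. The rule in 13.4 that counts dropouts as failures has no direct continuous equivalent, so the change needs its own missing-data rule.

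**Stronger readings that the documents do not support.**

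- A reader might infer that the planned model will often separate or fail to converge. That holds only near 8 covariates, and the plan states no number. Objective 4.3.2 describes characteristics; it does not specify a model.
- A reader might infer that the predictor hypothesis in Section 3 is undermined. That hypothesis compares women who do and do not reach 5% with 2 months of behavioural intervention, so it rests on the 2-month model in all 55 women.
- A reader might take 7 to 9 events as a forecast. The 29% is a design alternative, and even at that rate the chance of 7 to 9 events is 0.45.

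**Conclusion.** The point holds as a cheap improvement limited to the second logistic model in 13.2. On the plan's own figures that model has about 9 events, or 7 at the success cut-off, with no cap on predictors.

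Under the assumed model, splitting the outcome at 5% roughly halves the power for one true predictor with 3 to 5 covariates. The gap between the methods follows from arithmetic and simulation. Its exact size depends on the correlation, the number of covariates and the true response rate, none of which the documents fix.

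The 2-month model is adequate at r = 0.5. The primary Simon test uses none of these regressions and is unaffected.

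**What to change.** In 13.2, for SLOW-BWL at 6 months:

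1. Add linear regression of percentage weight change from baseline to 6 months as the main predictor analysis, with at most about 3 covariates named in advance, 2-month loss among them.
2. Keep the logistic model of reaching 5% as support, fitted with Firth penalisation, because it matches the endpoint.
3. State that missing 6-month weights in the linear model are handled by the multiple imputation already named in 13.2, with a sensitivity analysis, and that the dropout rule in 13.4 does not carry over to this model.

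The cost is SAP wording, including the missing-data sentence. No new visits, measurements or participants are needed. Results will be read as percentage points lost rather than odds of reaching 5%. Power stays low for weak predictors, and a many-predictor model in 30 women would remain unreliable by either method, so the short list matters as much as the change of outcome.

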13.3 Early Stopping

Following the Simon's two-stage design, the study will be stopped early for futility if there is 1 or fewer woman who attain \geq 5% weight loss in the first 15 SLOW-BWL women.

APPENDIX A: ECOG Performance Status Scale

Score	Definition
0	Asymptomatic
1	Symptomatic, fully ambulatory
2	Symptomatic, in bed less than 50% of day
3	Symptomatic, in bed more than 50% of day, but not bedridden
4	Bedridden

APPENDIX B: Lifestyle Guidelines Handout

Goal: Lose 5% or more of your body weight at 2 months and maintain weight loss

1. Keep calories in moderation*

To lose weight, if you currently weigh:

Less than 170 pounds: Consume approximately 1200 calories each day 171-220 pounds: Consume approximately 1500 calories each day 221-270 pounds: Consume approximately 1800 calories each day More than 270 pounds: Consume approximately 2200 calories each day

*Calorie levels: There is not one specific number that's right for you all the time. Your calorie need may change depending on exercise, lifestyle and where you are in the weight loss process.

2. Exercise regularly

We recommend moderate intensity aerobic exercise 30 - 60 minutes for 5 - 7 days per week in bouts of at least 10 minutes. Start with 60 minutes per week and gradually increase each week so that at Week 21, you are reaching 180 minutes of aerobic exercise per week.

3. Weigh yourself weekly when trying to lose weight and daily to maintain weight loss.

When you do weigh yourself, enter it into the website. Be sure to do this at least once per week.

4. Keep track of your eating and exercise.

Daily track your food, beverage and exercise type and minutes and Log on to the Fitbit website at least once per week and enter all your tracking information. We understand that it may be challenging to track your food over a 24 hours period every day of the week. We encourage you to log 24 hours of what you eat at least 4 of 7 days of the week.

Fitbit device for monitoring physical activity (wear this on your non-dominant hand for a minimum of 4 of 7 days with 10 hours per day)

5. Be an active study participant

Attend data collection visits and complete surveys at week 8 and 6 month follow-up. Keep all appointments with your Coach and complete Learning Focuses before calls.

Other recommended guidelines

Follow one of two eating styles:

- 1) The DASH diet
 - Eat 7-12 servings of fruits and vegetables every day
 - Eat 2-3 servings of low-fat dairy foods every day
 - Eat 25% or less of your total calories from fat
- 2) The Mediterranean diet

3)

- Daily consumption of vegetables, fruits, whole grains and healthy fats
- Weekly intake of fish, poultry, beans and eggs
- Moderate portions of dairy products
- Limited intake of red meat and alcohol

Eat a low-sodium diet

• Eat 2400 mg or less of sodium each day

Limit alcohol intake

- Women: Drink no more than one drink per day
- Men: Drink no more than two drinks per day 1 drink=12 ounces beer, 5 ounces wine, or 1 jigger (1 ½ ounce) of 80-proof liquor

APPENDIX C: Weekly weight and symptom survey

During the behavioral intervention, coaches call patients weekly the first 3 months, followed by monthly for months 4-6. Patients will receive a REDCap survey on a weekly basis with the following question:

1) What is your v	weight this week?
*If patients have not o	completed this survey before the call with the coach, the coach may enter
the data that is conve	yed verbally.

During months 3-6, ALL study participants will continue with weekly survey, in addition to a question about any new symptoms:

2) During the past 7 days, have you experienced any new symptoms (such as abdominal pain, anxiety, constipation, diarrhea, dizziness, dry mouth, fatigue, gastroenteritis, headache, hot flush, insomnia, nausea, tremor, vomiting etc.)?

^{*}If patients have not completed this survey before the call with the coach, the coach may enter the data that is conveyed verbally.

^{**}The coordinator will review all new symptom entries in the REDCap survey on a weekly basis, and new symptoms will be reported to the PI for further evaluation.

